7.2 Adverse Event Characteristics

CTCAE term (AE description) and grade: The descriptions and grading scales found in the revised NCI Common Terminology Criteria for Adverse Events (CTCAE) version 4.0 will be utilized for AE reporting. All appropriate treatment areas should have access to a copy of the CTCAE version 4.0. A copy of the CTCAE version 4.0 can be downloaded from the CTEP web site
http://ctep.cancer.gov/protocolDevelopment/electronic_applications/ctc.htm.

For expedited reporting purposes only:

- AEs for the agent that are **bold and italicized** in the CAEPR (i.e., those listed in the SPEER column, Section 7.1) should be reported through CTEP-AERS only if the grade is above the grade provided in the SPEER.

Attribution of the AE:

- Definite – The AE is clearly related to the study treatment.
- Probable – The AE is likely related to the study treatment.
- Possible – The AE may be related to the study treatment.
- Unlikely – The AE is doubtfully related to the study treatment.
- Unrelated – The AE is clearly NOT related to the study treatment.

7.3 Expedited Adverse Event Reporting

7.3.1 Expedited AE reporting for this study must use CTEP-AERS (CTEP Adverse Event Reporting System), accessed via the CTEP Web site (<https://eapps-ctep.nci.nih.gov/ctepaers>). The reporting procedures to be followed are presented in the “NCI Guidelines for Investigators: Adverse Event Reporting Requirements for DCTD (CTEP and CIP) and DCP INDs and IDEs” which can be downloaded from the CTEP Web site (http://ctep.cancer.gov/protocolDevelopment/electronic_applications/adverse_events.htm). These requirements are briefly outlined in the tables below (Section 7.3.3).

In the rare occurrence when Internet connectivity is lost, a 24-hour notification is to be made to CTEP by telephone at [contact]. Once Internet connectivity is restored, the 24-hour notification phoned in must be entered electronically into CTEP-AERS by the original submitter at the site.

7.3.2 Distribution of Adverse Event Reports

CTEP-AERS is programmed for automatic electronic distribution of reports to the following individuals: Principal Investigator and Adverse Event Coordinator(s) (if applicable) of the Corresponding Organization, the local treating physician, and the Reporter and Submitter. CTEP-AERS provides a copy feature for other e-mail recipients.

The Coordinating Center of the Corresponding Organization is responsible for submitting to the CTSU documentation of AEs that they deem reportable for posting on the CTSU protocol web page and inclusion on the CTSU bi-monthly broadcast.

7.3.3 Expedited Reporting Guidelines

Use the NCI protocol number and the protocol-specific patient ID assigned during trial registration on all reports.

Note: A death on study requires both routine and expedited reporting regardless of causality, unless as noted below. Attribution to treatment or other cause must be provided.

Death due to progressive disease should be reported as **Grade 5 “Neoplasms benign, malignant and unspecified (including cysts and polyps) - Other (Progressive Disease)”** under the system organ class (SOC) of the same name. Evidence that the death was a manifestation of underlying disease (e.g., radiological changes suggesting tumor growth or progression: clinical deterioration associated with a disease process) should be submitted.

Phase 1 and Early Phase 2 Studies: Expedited Reporting Requirements for Adverse Events that Occur on Studies under an IND/IDE within 30 Days of the Last Administration of the Investigational Agent/Intervention ^{1,2}

FDA REPORTING REQUIREMENTS FOR SERIOUS ADVERSE EVENTS (21 CFR Part 312)

NOTE: Investigators **MUST** immediately report to the sponsor (NCI) **ANY** Serious Adverse Events, whether or not they are considered related to the investigational agent(s)/intervention (21 CFR 312.64)
An adverse event is considered serious if it results in **ANY** of the following outcomes:

- 1) Death
- 2) A life-threatening adverse event
- 3) An adverse event that results in inpatient hospitalization or prolongation of existing hospitalization for ≥ 24 hours
- 4) A persistent or significant incapacity or substantial disruption of the ability to conduct normal life functions
- 5) A congenital anomaly/birth defect.
- 6) Important Medical Events (IME) that may not result in death, be life threatening, or require hospitalization may be considered serious when, based upon medical judgment, they may jeopardize the patient or subject and may require medical or surgical intervention to prevent one of the outcomes listed in this definition. (FDA, 21 CFR 312.32; ICH E2A and ICH E6).

ALL SERIOUS adverse events that meet the above criteria **MUST** be immediately reported to the NCI via electronic submission within the timeframes detailed in the table below.

Hospitalization	Grade 1 and Grade 2 Timeframes	Grade 3-5 Timeframes
Resulting in Hospitalization ≥ 24 hrs	10 Calendar Days	24-Hour 5 Calendar Days
Not resulting in Hospitalization ≥ 24 hrs	Not required	

NOTE: Protocol specific exceptions to expedited reporting of serious adverse events are found in the Specific Protocol Exceptions to Expedited Reporting (SPEER) portion of the CAEPR.

Expedited AE reporting timelines are defined as:

- "24-Hour; 5 Calendar Days" - The AE must initially be submitted electronically within 24 hours of learning of the AE, followed by a complete expedited report within 5 calendar days of the initial 24-hour report.
- "10 Calendar Days" - A complete expedited report on the AE must be submitted electronically within 10 calendar days of learning of the AE.

¹Serious adverse events that occur more than 30 days after the last administration of investigational agent/intervention and have an attribution of possible, probable, or definite require reporting as follows:

Expedited 24-hour notification followed by complete report within 5 calendar days for:

- All Grade 3, 4, and Grade 5 AEs

Expedited 10 calendar day reports for:

- Grade 2 AEs resulting in hospitalization or prolongation of hospitalization

²For studies using PET or SPECT IND agents, the AE reporting period is limited to 10 radioactive half-lives, rounded UP to the nearest whole day, after the agent/intervention was last administered. Footnote "1" above applies after this reporting period.

Effective Date: May 5, 2011

7.3.4 Additional Protocol-Specific Expedited Adverse Event Reporting Exclusions
None.

7.4 Routine Adverse Event Reporting

All Adverse Events **must** be reported in routine study data submissions. **AEs reported expeditiously through CTEP-AERS must also be reported in routine study data submissions.**

Adverse event data collection and reporting, which are required as part of every clinical trial, are done to ensure the safety of patients enrolled in the studies as well as those who will enroll in future studies using similar agents. AEs are reported in a routine manner at scheduled times during the trial using Medidata Rave.

7.5 Secondary Malignancy

A secondary malignancy is a cancer caused by treatment for a previous malignancy (e.g., treatment with investigational agent/intervention, radiation or chemotherapy). A secondary malignancy is not considered a metastasis of the initial neoplasm.

CTEP requires all secondary malignancies that occur following treatment with an agent under an NCI IND/IDE be reported expeditiously via CTEP-AERS. Three options are available to describe the event:

- Leukemia secondary to oncology chemotherapy (e.g., acute myelocytic leukemia [AML])
- Myelodysplastic syndrome (MDS)
- Treatment-related secondary malignancy

Any malignancy possibly related to cancer treatment (including AML/MDS) should also be reported via the routine reporting mechanisms outlined in each protocol.

Indicate form for reporting in Rave, timeframes, and if loading of the pathology report is required.

7.6 Second Malignancy

A second malignancy is one unrelated to the treatment of a prior malignancy (and is **NOT** a metastasis from the initial malignancy). Second malignancies require **ONLY** routine AE reporting unless otherwise specified.

8. PHARMACEUTICAL INFORMATION

A list of the adverse events and potential risks associated with the investigational administered in this study can be found in Section 7.1.

8.1 CTEP IND Agent(s)

8.1.1 Nivolumab (NSC 748726)

Amino Acid Sequence: 4 polypeptide chains, which include 2 identical heavy chains with 440 amino acids and 2 identical light chains.

Other Names: BMS-936558, MDX1106

Classification: Anti-PD-1MAb

M.W.: 146,221 Daltons

Mode of Action: Nivolumab targets the programmed death-1 (PD-1, cluster of differentiation 279 [CD279]) cell surface membrane receptor. PD-1 is a negative regulatory receptor expressed by activated T and B lymphocytes. Binding of PD-1 to its ligands, programmed death-ligand 1 (PD-L1) and 2 (PD-L2), results in the down-regulation of lymphocyte activation. Nivolumab inhibits the binding of PD-1 to PD-L1 and PD-L2. Inhibition of the interaction between PD-1 and its ligands promotes immune responses and antigen-specific T-cell responses to both foreign antigens as well as self-antigens.

Description: Nivolumab Injection is a clear to opalescent, colorless to pale yellow liquid; light (few) particulates may be present. The drug product is a sterile, nonpyrogenic, single-use, isotonic aqueous solution formulated in sodium citrate, sodium chloride, mannitol, diethylenetriamine pentacetic acid (pentetic acid) and polysorbate 80 (Tween® 80), pH 6.0.

How Supplied: Nivolumab is supplied by Bristol-Myers Squibb and distributed by the Pharmaceutical Management Branch, CTEP/DCTD/NCI as 100 mg vials (10 mg/mL) with a 0.7 mL overfill. It is supplied in 10 mL type I flint glass vials, with butyl rubber stoppers and aluminum seals.

Preparation: Nivolumab injection can be infused undiluted (10 mg/mL) or diluted with 0.9% Sodium Chloride Injection, USP or 5% Dextrose, USP to concentrations no less than 0.35 mg/mL.

Storage: Vials of Nivolumab injection must be stored at 2°-8°C (36°-46°F) and protected from light, freezing, and shaking.

Stability: Shelf-life surveillance of the intact vials is ongoing.

The administration of undiluted and diluted solutions of Nivolumab must be completed within 24 hours of preparation. If not used immediately, the infusion solution may be stored up to 24 hours in a refrigerator at 2°-8°C (36°-46°F) and a maximum of 4 hours of the total 24 hours can be at room temperature (20°-25°C, 68°-77°F) and room light. The maximum 4-hour period under room temperature and room light conditions includes the product administration period.

CAUTION: The single-use dosage form contains no antibacterial preservative or bacteriostatic agent. Therefore, it is advised that the product be discarded 8 hours after initial entry.

Route of Administration: Intravenous infusion. Do not administer as an IV push or bolus injection. NOTE REF TO DOSING SCHEDULE

Method of Administration: Administer through a 0.2 micron to 1.2 micron pore size, low-protein binding polyethersulfone membrane in-line filter.

Potential Drug Interactions: No incompatibilities between Nivolumab injection and polyvinyl chloride (PVC), non-PVC/non-DEHP (di[2-ethylhexyl]phthalate) IV components, or glass bottles have been observed.

Availability: Nivolumab is an investigational agent supplied to investigators by the Division of Cancer Treatment and Diagnosis (DCTD), NCI.

Nivolumab is provided to the NCI under a Collaborative Agreement between the Pharmaceutical Collaborator and the DCTD, NCI (see Section 12.3).

8.1.2 Agent Ordering and Agent Accountability

8.1.2.1 NCI-supplied agents may be requested by the Principal Investigator (or their authorized designee) at each participating institution. Pharmaceutical Management Branch (PMB) policy requires that agent be shipped directly to the institution where the patient is to be treated. PMB does not permit the transfer of agents between institutions (unless prior approval from PMB is obtained). The CTEP-assigned protocol number must be used for ordering all CTEP-supplied investigational agents. The responsible investigator at each participating institution must be registered with CTEP, DCTD through an annual submission of FDA Form 1572 (Statement of Investigator), Curriculum Vitae, Supplemental Investigator Data Form (IDF), and Financial Disclosure Form (FDF). If there are several participating investigators at one institution, CTEP-supplied investigational agents for the study should be ordered under the name of one lead investigator at that institution.

Active CTEP-registered investigators and investigator-designated shipping designees and ordering designees can submit agent requests through the PMB Online Agent Order Processing (OAOP) application (<https://eapps-ctep.nci.nih.gov/OAOP/pages/login.jspx>). Access to OAOP requires the establishment of a CTEP Identity and Access Management (IAM) account (<https://eapps-ctep.nci.nih.gov/iam/>) and the maintenance of an “active” account status and a “current” password. For questions about drug orders, transfers, returns, or accountability, call [contact] Monday through Friday between 8:30 am and 4:30 pm (ET) or email [contact] anytime.

8.1.2.2 Agent Inventory Records – The investigator, or a responsible party designated by the investigator, must maintain a careful record of the inventory and disposition of all agents received from DCTD using the NCI Drug Accountability Record Form (DARF). (See the NCI Investigator’s Handbook for Procedures for Drug Accountability and Storage.)

9.1.2 Mandatory Baseline Serum Lymphocyte Count

The baseline absolute lymphocyte count result will be collected during routine blood sampling for differential white cell count. This value will be correlated with response.

9.2 Exploratory/Ancillary Correlative Studies

9.2.1 Plasma EBV DNA Clearance

9.2.1.1 Hypothesis: We hypothesize that plasma EBV DNA half-life during the first 6 weeks of treatment may be associated with subsequent RECIST-response to nivolumab.

9.2.1.2 Collection of Specimen(s):

This test is **mandatory** for all enrolled subjects. 3-5ml of EDTA blood sample (x 1 tube) will be taken at baseline (within 7 days of starting the first dose of study drug), and then at weekly interval: week 1 (day 7 +/- 2 days), week 3 (day 21 +/- 2 days), week 4 (day 28 +/- 2 days), week 5 (day 35 +/- 2 days) and week 6 (day 42, +/- 2 days). Week 2 sampling is omitted given the possibility of a surge in level. Consecutive samples can only be taken with no more than 5 to 9 days apart.

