9.2.3 Monitoring of Inflammatory Cytokines during Nivolumab Therapy

9.2.3.1 Hypothesis: Nivolumab may affect the level of inflammatory cytokines (e.g. IFN- γ , TNF- α , IL-6) and immune cell levels in nasopharyngeal carcinoma.

9.2.3.2 Sample collection: This blood sampling is mandatory for all patients enrolled into this study. 5 ml of EDTA blood will be collected at baseline, and just prior to nivolumab dosing on week 3 (\pm 2 days), week 5 (\pm 2 days) and week 7 (\pm 2 days). The blood sampling schedules should coincide with the plasma EBV DNA blood samples (section 9.2.1) or routine bloods (see section 10), where applicable.

9.2.3.3 Sample processing: same as section 9.2.1.3.

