9.2.3.4 Shipment: same as section 9.2.1.4

10. STUDY CALENDAR

	Pre-Study	Wk 1	Wk 2	Wk 3	Wk 4	Wk 5	Wk 6	Wk 7	Wk 8	Wk 9	Wk 10	Wk 11, etc	Wk 16	Off Study ^c
B-HCG	X ^b													
Archived tumor retrieval or fresh tissue collected by biopsy (Mandatory) ^R	X ^f													
Plasma EBV DNA blood sampling (Mandatory) ^{h,R}	X*	X*		X	X	X	X							
Plasma cytokine level ^{h, R}	X			X		X		X						
MRI study (Optional for Hong Kong site only) ^R	X ^g			X			X		X				X	
HIV, hepatitis B and C serology ^j	X													

Baseline blood tests are to be conducted within 1 week prior to start of protocol therapy except for the HIV, hepatitis B and C serology which may be done within 4 weeks prior to starting study treatment. Scans and x-rays must be done < 4 weeks prior to the start of therapy. In the event that the patient's condition is deteriorating, laboratory evaluations should be repeated within 48 hours prior to initiation of the next cycle of therapy. All visits may be held within \pm 2 days of scheduled visit.

A: Administration schedule of nivolumab

- a: Baseline chemistry: Albumin, alkaline phosphatase, total bilirubin, urea, calcium, creatinine, fasting glucose, LDH, phosphorus, potassium, total protein, SGPT [ALT] (or AST if available at the center), sodium, TSH (with reflexive Free T4 and Free T3), amylase. (* The tests done at 'pre-study' period can be used as 'week 1' bloods as long as they are done within 7 days of the 1st dose. Baseline serum absolute lymphocyte count will be collected.)
- b: A serum or urine pregnancy testing is required within 24 hrs of study enrollment.
- c: Off-study evaluation should be performed within 30 days of coming off study. Should reinforce criteria for follow up for 100 days for AE assessment.

- d: Laboratory tests to be done within 72 hrs prior to re-dosing: CBC w/ differential, LFTs, serum urea and creatinine, Ca, Mg, Na, K, LDH, random glucose, amylase.
- e: Laboratory tests to be done every 4 weeks: TSH (with reflexive Free T4 and Free T3)
- f: Retrieval of archived tumor block/ unstained slides is mandatory. Each site should retrieve the specimen within 4 weeks of study registration. If a patient does not have archived tissue available, a fresh tissue sample must be obtained by biopsy at this time.

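### The 5-to-9-day spacing rule for plasma EBV DNA cannot be met between week 1 and week 3, and the calendar's asterisk permits baseline to replace the mandatory day-7 sample

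*Combined protocol and SAP*

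**What the plan says.** Section 9.2.1.2 makes the EBV DNA test mandatory. Blood "will be taken at baseline (within 7 days of starting the first dose of study drug"), and then at "week 1 (day 7 +/- 2 days), week 3 (day 21 +/- 2 days), week 4 (day 28 +/- 2 days"), day 35 ± 2 and day 42 ± 2. The gap in the series is intended: "Week 2 sampling is omitted given the possibility of a surge in level". The next sentence is the spacing rule: "Consecutive samples can only be taken with no more than 5 to 9 days apart". It makes no exception for the skipped week. Section 9.2.1.3, on labelling, still includes week 2 among its example sample labels.

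In the section 10 calendar, the row "Plasma EBV DNA blood sampling (Mandatory") has X* under Pre-Study and Wk 1, nothing under Wk 2, and X under Wk 3 to 6. The asterisk is explained inside note a, the baseline chemistry note, which says that pre-study tests "can be used as 'week 1' bloods as long as they are done within 7 days of the 1st dose". Note h, attached to the EBV row, refers the reader to 9.2.1.2 for timing.

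Section 9.2.3.2 sets the cytokine draws: "5 ml of EDTA blood will be collected at baseline, and just prior to nivolumab dosing on week 3", and likewise in weeks 5 and 7, each ±2 days. It adds "The blood sampling schedules should coincide with the plasma EBV DNA blood samples (section 9.2.1"), and the same sentence goes on to offer routine bloods as an alternative, where applicable. Section 5.1.1 places doses on days 1 and 15 of a 4-week cycle.

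**The concern.** Correlative objective 1.3.1 and hypothesis 9.2.1.1 rest on early EBV DNA clearance, and section 13.4.6 correlates the half-life over the first 6 weeks with RECIST response. Three instructions about when to draw the blood do not fit together.

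- A site that tries to obey the spacing rule must either draw in the week the protocol chose to avoid or move the week 3 sample out of its window. A site that follows the schedule records a deviation for every patient.
- The calendar can be read as letting the baseline tube count as week 1. The day-7 sample is the only one between baseline and week 3. If it is not drawn, nothing in the analysis can restore it.
- The EBV and cytokine rows use the same week numbers for different days, so sites may collect samples under one label at different times.

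**Working it through.** **Inputs.** EBV windows from 9.2.1.2, in days from first dose: baseline −7 to 0, week 1 = 5–9, week 3 = 19–23, week 4 = 26–30, week 5 = 33–37, week 6 = 40–44. Spacing limit from the same section: 5 to 9 days. Dose days from 5.1.1: 1, 15, 29, 43. Cytokine window from 9.2.3.2: dose day ± 2. Counting the first dose as day 1 instead of day 0 moves the gaps that involve baseline by one day and leaves the week 1 to week 3 gap unchanged.

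**Step 1: spacing.** For each consecutive pair, the shortest gap is the later window's first day minus the earlier window's last day. The longest gap is the later window's last day minus the earlier window's first day. All whole-day combinations were counted.

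| Pair | Shortest gap | Longest gap | Combinations within 5–9 days |
|---|---|---|---|
| Baseline to week 1 | 5 − 0 = 5 | 9 − (−7) = 16 | 15 of 40 |
| Week 1 to week 3 | 19 − 9 = 10 | 23 − 5 = 18 | 0 of 25 |
| Week 3 to week 4 | 26 − 23 = 3 | 30 − 19 = 11 | 19 of 25 |
| Week 4 to week 5 | 33 − 30 = 3 | 37 − 26 = 11 | 19 of 25 |
| Week 5 to week 6 | 40 − 37 = 3 | 44 − 33 = 11 | 19 of 25 |

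The week 1 to week 3 pair fails in every case, even if only the 9-day upper limit is applied. The other four pairs can all meet the rule.

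**Step 2: the asterisk.** The asterisk text accepts a pre-study test done within 7 days of the first dose. Section 9.2.1.2 defines the EBV baseline by the same 7 days, so every compliant baseline qualifies as a substitute. If the substitution is made, the first on-treatment sample is week 3, on days 19–23. The gap from baseline is then 19 − 0 = 19 to 23 − (−7) = 30 days. Baseline and weeks 3 to 6 remain, which is five of the six scheduled samples.

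**Step 3: two meanings of weeks 3 and 5.**

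- Week 3: the pre-dose cytokine draw is day 15 ± 2 = 13–17 and the EBV draw is days 19–23. No day is shared.
- Week 5: the pre-dose cytokine draw is day 29 ± 2 = 27–31 and the EBV draw is days 33–37. No day is shared.
- Omitted week 2: the protocol gives no window. Taking day 14 ± 2 by analogy gives 12–16, which overlaps the week 3 pre-dose window on days 13–16.

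An EBV tube drawn at the week 3 dosing visit would therefore fall in or next to the omitted week.

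**The case against.** **The exception is obvious from context.** The sentence before the spacing rule skips week 2, so a sensible reader would excuse the longer gap. That is fair, and no sample is lost through the spacing rule alone. It remains a written requirement, on a mandatory test, that no patient can satisfy.

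**The calendar does not remove day 7.** A reader might infer that its week numbering does. The documents do not support that. With the first dose on day 1, day 7 is the last day of calendar week 1, and days 21, 28, 35 and 42 are the last days of weeks 3 to 6, so the numbering fits 9.2.1.2. Note h also sends sites there. The asterisk text is permissive and sits in a chemistry note. Other rows of the calendar are not legible in the text reviewed, so its intended scope cannot be fully checked. What stands is that the asterisks are on the EBV row itself, and the sites are left with two answers.

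**The draws need not clash.** A reader might also infer that 9.2.3.2 forces EBV sampling into the surge. It does not: the sentence governs the cytokine draws and allows alignment with routine bloods, which note d already requires within 72 hours before re-dosing. Moving EBV to day 15 would breach 9.2.1.2. The days on which a surge might occur are inferred, not stated. Only a risk of misreading remains.

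**The size of any distortion is not known.** Section 2.4 gives a half-life of 3.8 days, at which a 6-day shift (21 − 15) means a factor of 2^(6/3.8) ≈ 3.0. After 21 days, 2^(−21/3.8) ≈ 2% would remain, so about 98% would have cleared. That half-life comes from radiotherapy and surgery. The 8-day threshold in the same section comes from chemotherapy and is not adopted for the analysis here. Neither can be carried over to nivolumab. Collection dates are recorded under 9.2.1.3, so a mistimed sample can be analysed at its true day. A sample never drawn cannot.

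**Conclusion.** The spacing contradiction is certain and rests on 9.2.1.2 alone: a gap of 10 to 18 days against a limit of 9. The possible loss of day 7 is a real ambiguity. It depends on a site reading the asterisk as covering the EBV row, and its effect would be no on-treatment EBV DNA value before day 19. The double meaning of weeks 3 and 5 is a lesser risk that depends on a site combining draws.

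No numerical bias in the half-life can be claimed from the documents. The consequences are confined to an exploratory correlative objective (1.3.1, 9.2.1.1). The primary endpoint, interim rule, sample size and safety monitoring are untouched. The plan should be corrected because the defect affects which samples exist and costs little to remove.

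**What to change.** 1. In 9.2.1.2, exempt the week 1 to week 3 pair from the 5-to-9-day rule. Keep the rule for the 7-day pairs: baseline to week 1, and weeks 3–4, 4–5 and 5–6. Baseline to week 1 should stay under the rule because it can comply.
2. In section 10, remove the asterisk from the Wk 1 EBV cell, or state that the pre-study draw does not replace the day-7 sample.
3. In 9.2.1.2, 9.2.3.2 and section 10, give the research draws by study day: EBV DNA at baseline and days 7, 21, 28, 35 and 42; cytokines at baseline and pre-dose on days 15, 29 and 43. State that the week 3 and week 5 cytokine draws align with routine pre-dose bloods, not with the EBV draws.
4. Delete the week 2 label from 9.2.1.3.
5. In 13.4.6, compute the half-life from actual days since first dose.

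The cost is wording and a calendar revision, with no tube beyond those already required. The small downside is that EBV and cytokine draws do not share a visit at weeks 3 and 5.
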